3.2.9. Penn Physician Withdrawal Checklist

The PWC is a 20-item scale to measure discontinuation symptoms (e.g., loss of appetite, nausea-vomiting, diarrhea, anxiety-nervousness, irritability, etc.) after stopping a medication for anxiety disorders ([Rickels et al, 2008](#)). All 20 items are rated on a 4-point numeric-rating scale ranging from 0 (not present), 1 (mild), 2 (moderate), to 3 (severe). A total score, ranging from 0 to 60, can be calculated in addition to the individual scores for each item. If more than 4 individual items are missing, the PWC total score will not be calculated and will be left as missing. If less than or equal to 4 individual item scores are missing, the missing item scores will be imputed by the mean of all other available item scores or the maximum possible values for the missing responses, whichever is smaller, to calculate the PWC total score. Lower scores indicate less severity in discontinuation symptoms.

3.3. Pharmacokinetics

With participants maintaining their normal BID dosing routine, a single daytime venous blood sample for determination of plasma darigabat concentration will be collected as specified in the Schedule of Assessments.

During each PK sampling, an approximately 4-mL venous blood sample will be collected into appropriately labeled tubes. The blood samples will be used to provide approximately 2×1 -mL plasma samples (one primary and the other as backup) for separate quantifications in plasma.

A fully validated bioanalytical method will be used to quantitate the concentrations of darigabat in plasma. Plasma samples collected in this trial may be used for further development of the bioanalytical method or identification of metabolites. The backup samples may be stored for a duration of approximately up to 1 year after the date of the final CSR.

3.4. Other Assessments

3.4.1. Sheehan Disability Scale

The Sheehan Disability Scale (SDS) instrument is patient rated with the first 3 items in a numeric rating scale and the last 2 questions asking for number of days impacted ([Sheehan et al, 1996](#); [Sheehan, 1983](#)). The first 3 items, one for each of the 3 domains, are rated on an 11-point numeric rating scale ranging from 0 (not at all), 1 to 3 (mildly), 4 to 6 (moderately), 7 to 9 (markedly), to 10 (very severely). The sum score from the first 3 items, ranging from 0 (unimpaired) to 30 (highly impaired), will be used to evaluate global functional impairment.

Individual subscores from the first 3 items will also be reported to assess the impact of panic disorder on work, social life/leisure activities, and family life/home responsibilities.

Two additional items measuring “days lost” and “days unproductive” during the last week further quantify the lost and reduced productivity in school or work.

If one item is missing to evaluate global functional impairment, the scores from the other two items will be averaged and used in the summation. If two or more items are missing, then the SDS total score will be missing.

3.4.2. European Quality of Life (EQ-5D-5L)

The European Quality of Life (EQ-5D-5L) is a generic estimate of health status with 2 parts ([EQ-5D-5L User Guide, 2019](#)). The first part, the descriptive system, was designed to assess decrement of health in terms of 5 domains: mobility, self-care, usual activities, pain/discomfort, and anxiety/depression. Each of these dimensions has a self-rated 5 level response: no problem (level 1), slight problems (level 2), moderate problems (level 3), severe problems (level 4), and unable to/extreme problems (level 5). Thus, a health profile consisting of a 5-digit code based on respondent’s selected levels for each of the 5 dimensions will be generated. For example, a respondent with a health profile code of 12345 would have no problem with mobility, slight problems with self-care, moderate problems with usual activities, severe problems with pain/discomfort, and extreme problems with anxiety/depression. For each participant and visit, the 5-digit health state will be converted into a single summary index, the EQ-5D Index, using the EQ-5D-5L Index calculator with US value set ([van Hout et al, 2012](#)).

The second part of EQ-5D-5L is the EQ Visual Analog Scale (EQ VAS), a self-rated vertical visual analog scale (VAS). The VAS is numbered from 0 to 100 with 0 meaning ‘the worst health you can imagine’ and 100 meaning ‘the best health you can imagine’. This information can be used as a quantitative measure of health outcome that reflects the patient’s own judgement. The EQ-5D-5L asks respondents to simply ‘mark an X on the scale to indicate how your health is TODAY’ and then to ‘write the number you marked on the scale in the box below’.

4. DATA CONVENTIONS AND VISIT WINDOWS

4.1. Data Conventions

4.1.1. Age

Age is the age at the time of informed consent and is as captured on the eCRF.

4.1.2. Day 1

Study Day 1 is the day IMP is first initiated.

4.1.3. Study Day of an Event

Study day of an event is defined relative to study day 1 as:

Study Day = event date – date of study day 1 (+ 1, if event date \geq date of study day 1).

This calculation will result in negative study days for an event occurring prior to the start of IMP and positive study days for an event on or after the start of IMP. There will be no Day 0 value to match the schedule of events.

4.1.4. Days on Study

Days on study is the number of days from Day 1 to the date of study completion or early termination as recorded on the END OF STUDY CRF.

4.1.5. Days on Treatment

Days on study is the number of days from Day 1 to the date of study completion or early termination as recorded on the END OF STUDY CRF.

4.1.6. Date of Diagnosis

Date of Initial Diagnosis will be taken from the Mini International Neuropsychiatric Interview CRF. Partial dates will be imputed as instructed in [Section 4.1.19](#).

4.1.7. Years Since Initial Diagnosis

Years since initial diagnosis will be calculated as the difference between the date of Informed Consent and the date of Initial Diagnosis.

4.1.8. Days on IMP

Days on IMP is the number of days from Study Day 1 to the date of last dose of IMP as recorded on the END OF TREATMENT CRF.

4.1.9. Baseline Value

The baseline value is defined as the last non missing value obtained prior to initiation of the first dose of IMP.

For blood pressure and heart rate measurements, baseline is defined as the average of the duplicates at the last visit prior to the IMP administration. If no duplicate is available, the last non-missing value prior to the initiation of IMP will be used.

The panic attack frequency recorded for the 14 days prior to randomization and dosing will be used as the baseline.

4.1.10. Change from Baseline

Change from baseline for a given endpoint is defined as the value on a given Study Day minus the Baseline Value.

4.1.11. Orthostatic Change

Orthostatic change is calculated as the difference in the standing value from the supine value (i.e., supine value – standing value). If an average value is available at a given visit, date and timepoint, it will be used for the calculation of orthostatic change. If an average value is not available, the individual record obtained on a given visit, date, and timepoint will be used.

4.1.12. Last Dose of IMP

Last Dose of IMP is defined as the last date that the participant received IMP.

4.1.13. Last Two Weeks of Maintenance Treatment

The last two weeks of maintenance treatment for an individual participant is defined as the 14 days leading up to and including the last dose of IMP. For aggregate analysis, the last two weeks of maintenance treatment is defined as two weeks prior to Visit 6 (Week 14). A participant must have a minimum of 14 days of treatment in the maintenance phase to be considered for this metric.

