4.1.18. Definition of Completed Participant

A participant is considered to be a treatment completer if he/she has completed the Treatment Period of the trial including the last visit in the Maintenance Treatment Period (Visit 6, Day 98) as captured in the eCRF.

A participant is considered to have completed the study if he/she has completed all periods of the trial including the last scheduled procedure in the Safety Follow-up (Visit 9, Day 131) as shown in the Schedule of Assessments in [Section 9.1](#) and as captured in the eCRF.

Table 3: Two-Week Intervals

Two-Week Interval	Study Days in Interval
Maintenance Week 1-2	Days 15-28
Maintenance Week 3-4	Days 29-42
Maintenance Week 5-6	Days 43-56
Maintenance Week 7-8	Days 57-70
Maintenance Week 9-10	Days 71-84
Maintenance Week 11-12 (no-panic attack endpoint)	Two weeks prior to end of treatment
Maintenance Week 11-12 (panic attack frequency endpoint)	Days 85-last day in treatment period

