5.11. Primary Efficacy Analysis

5.11.1. Primary Analysis

The primary estimand has the following attributes:

1. Treatments as randomized
2. The population defined by the inclusion/exclusion criteria of the trial as the primary population of interest
3. The proportion of participants who are free of panic attacks during the last two weeks of the Maintenance Treatment as the primary endpoint of interest
4. The population level summary of interest is the estimated odds ratio of freedom from panic attack between treatments and the corresponding 95% confidence intervals (CI)
5. Handling of intercurrent events (ICEs)
 - The treatment policy strategy will be used to handle the ICE of use of concomitant medications during the study for primary analysis of the primary efficacy endpoint, which will include the collected data in the analyses regardless of the use of medications
 - The hypothetical strategy will be used to handle the ICEs of discontinuation from treatment/study participation for primary analysis of the primary efficacy endpoint, which will only include collected data through the discontinuation visit

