6. CHANGES IN THE PLANNED ANALYSES

Analysis methods described here reflect revisions to strategic focus and scope and will supersede those described in the protocol. In addition to changes corresponding to protocol amendments, the analysis plan differs from the statistical analysis section of the protocol as described below:

- As a result of early closure of enrollment and early treatment discontinuation of ongoing participants, planned sample size will not be achieved and proportion of participants with treatment discontinuation will be increased. The resulting sample size will have insufficient power for hypothesis tests and thus, efficacy analysis will be exploratory.
 - The following changes were made to the protocol-specified statistical analysis to reflect the strategic shift to an exploratory evaluation of efficacy
 - Multiplicity adjustments were removed
 - Most sensitivity analyses were removed
 - Supportive analyses involving panic attack-related endpoints were added using an expanded FAS population including all participants regardless of eDiary version used
- Description of handling of ICEs was expanded and revised for the primary and key secondary endpoints:
 - Additional detail was provided for different types of ICEs (eg, administration of rescue medication and treatment discontinuation)
 - Composite strategy was replaced with treatment policy and while on treatment strategies for handling ICEs for analysis of primary and key secondary endpoints
- Added description of missing diary data handling:
 - For the primary efficacy outcome (proportion of participants free of panic attacks), outcome for participants who did not report a panic attack and had <12/14 days of completed eDiary was set to missing, unless otherwise indicated
 - For key secondary efficacy outcome (change from baseline in the frequency of panic attacks), outcome for participants with <7/14 days of completed eDiary was set to missing
- The SAP replaced the SAS® procedure GLIMMIX (specified in protocol) with GENMOD to fit binomial repeated measures model to estimate the proportion of participants that were free of panic attack and the treatment difference. Although both procedures can fit binomial repeated measures model, model-fitting is more efficient with the GENMOD procedure.

Should any deviations from the analyses pre-specified in the authorized statistical analysis plan arise, such deviations will be documented in the final clinical study report.

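### The SAP gives conflicting windows for the primary Week 11-12 panic-free outcome, and the one in Table 3 scores early stoppers on earlier on-treatment days, which does not fit the declared hypothetical strategy

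*SAP*

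**What the plan says.** **Window.** SAP 4.1.13 gives two definitions in consecutive sentences. For an individual, the last two weeks of maintenance are "defined as the 14 days leading up to and including the last dose of IMP". The next sentence reads "For aggregate analysis, the last two weeks of maintenance treatment is defined as two weeks prior to Visit 6 (Week 14"). It then limits entry: "A participant must have a minimum of 14 days of treatment in the maintenance phase to be considered for this metric".

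Table 3 (under SAP 4.1.18) gives fixed study days for the five intervals from Day 15 to Day 84. The last slot has two rows. The row "Maintenance Week 11-12 (no-panic attack endpoint") is filled with "Two weeks prior to end of treatment". The row for the frequency endpoint is filled with "Days 85-last day in treatment period".

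SAP 5.11.2 takes the odds ratio at the endpoint analysis period of a GENMOD repeated-measures model. If sparse data make that fit unreliable, conclusions move to the Fisher test in 5.11.3, which scores the final two weeks of treatment within maintenance.

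**Strategy.** SAP 5.11.1 states: "The hypothetical strategy will be used to handle the ICEs of discontinuation from treatment/study participation", using data through the discontinuation visit. The summary in 5.13 agrees. SAP Section 6 says, for the primary and key secondary endpoints together: "Composite strategy was replaced with treatment policy and while on treatment strategies". It does not mention the hypothetical strategy.

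**Diary rule.** Under SAP 3.1.1.2, an attack-free participant needs at least 12 completed diary days in the interval; otherwise the outcome is missing.

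**The concern.** A hypothetical strategy asks what the Week 11-12 outcome would have been had treatment continued. For someone who stopped earlier that outcome is unobserved, and the model has to supply it. Filling the slot with the last 14 on-treatment days answers a different question: how the participant was doing when treatment ended, whenever that was. Inside a repeated-measures model the same diary days can also appear twice, once in their own calendar interval and once as Week 11-12.

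Two programmers working from this SAP could derive different primary outcomes. This matters more than usual here because Section 6 expects early closure to increase the proportion who discontinue treatment. It gives no figure.

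**Working it through.** **1. The plan's own figure.** SAP 1.2 plans 114 per group, 60% versus 40%, two-sided 0.05, power at least 80%. By the pooled normal formula, z = (0.20 × √114 − 1.96 × √0.50) / √0.48 = (2.135 − 1.386) / 0.693 = 1.08, so power is 86%. Exact Fisher power is 84%. The statement holds. The planned odds ratio is (0.6/0.4) / (0.4/0.6) = 2.25.

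**2. How early the window can fall.** Maintenance starts on Day 15 and 14 maintenance days are required, so the earliest qualifying stop is Day 28 and the earliest window is Days 15-28. That window ends 98 − 28 = 70 days before Day 98.

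**3. One example.** Last dose on Day 45: the window is Days 32-45. Days 32-42 (11 days) also lie in maintenance Weeks 3-4. Days 43-45 lie in Weeks 5-6, but with only 3 on-treatment days that interval is missing for an attack-free participant. So 11 of the 14 days are used twice.

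**4. Average double use.** Assume stop days uniform over Days 28-97 (70 days), full diaries up to the last dose and no attacks. There are 70 × 14 = 980 window days.

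- Let k be the days since the last complete interval ended. For k = 0 to 11 the running interval has fewer than 12 days and drops out, leaving 14 − k days used twice: 14 + 13 + … + 3 = 102.
- For k = 12 and 13 the running interval counts, so all 14 days are used twice: 28. Each 14-day cycle gives 130.
- Four cycles (stops on Days 28-83) give 520. Stops on Days 84-97 give 14 + 13 + … + 1 = 105.
- Total 625, and 625/980 = 64%.

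**5. Effect on the odds ratio.** Let d be the share of scored participants in an arm who stopped early and e their panic-free rate in the last 14 days on treatment. The slot rate is (1 − d) × Week 14 rate + d × e, with Week 14 rates of 60% and 40%. Neither d nor e is in the documents; the ranges are assumptions, with d equal in both arms. The mixture ignores covariates.

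| e, darigabat / placebo | d = 10% | 20% | 40% | 60% |
|---|---|---|---|---|
| 30% / 30% | 2.07 | 1.92 | 1.64 | 1.41 |
| 30% / 20% | 2.16 | 2.09 | 1.96 | 1.86 |
| 40% / 20% | 2.25 | 2.26 | 2.30 | 2.37 |
| 60% / 20% | 2.45 | 2.67 | 3.19 | 3.86 |

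Lowest cell: 0.4 × 0.60 + 0.6 × 0.30 = 0.42 and 0.4 × 0.40 + 0.6 × 0.30 = 0.34, so (0.42/0.58) / (0.34/0.66) = 1.41. Highest: 0.60 and 0.4 × 0.40 + 0.6 × 0.20 = 0.28, so (0.60/0.40) / (0.28/0.72) = 3.86.

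**6. Unequal stopping with no Week 14 effect.** Take 40% in both arms at Week 14, 20% in early stoppers, and stopping of 10% on darigabat and 30% on placebo. The slot rates are 0.38 and 0.34, odds ratio 1.19; with the arms reversed it is 0.84. Equal stopping gives 1.00.

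**The case against.** The best defence is the aggregate sentence in 4.1.13. An odds ratio is an aggregate analysis. If its window is the two weeks before Visit 6 at Week 14, early stoppers have no Week 11-12 record and the hypothetical strategy is respected. This is a fair reading, and it means carry-forward is not the settled rule. It does not clear the plan. Table 3 gives the panic-free row a different content from the frequency row beside it, 5.11.3 follows the moving window, and the schedule labels the Visit 6 day as either 98 or early termination, so even the aggregate window can move.

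Other limits also stand. Not every early stopper enters: 14 maintenance days are required, plus either an attack or at least 12 diary days. The Fisher test uses one outcome per participant, so nothing is counted twice there. A window tied to the end of treatment is not foreign to this trial, since the primary estimand in Protocol 9.3.2 refers to the two weeks before the intercurrent event, although under a composite strategy. Relabelling the estimand as while-on-treatment would also remove the conflict with Table 3.

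A reader might infer that Section 6 assigns while-on-treatment to the primary endpoint. It does not clearly do so: it lists strategies for several endpoints together, and while-on-treatment is the declared strategy for the second key secondary (5.12.2.1). Section 6 omits the hypothetical strategy and goes no further than that.

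**Conclusion.** The window and the strategy for the primary endpoint do not agree across SAP 4.1.13, Table 3, 5.11.1, 5.11.3 and 5.13, and Section 6 leaves the declared strategy out. Followed as written, Table 3 makes the endpoint period of the model a mixture of Week 14 outcomes and last-on-treatment outcomes from earlier dates. The resulting odds ratio depends on the timing and balance of stopping; 1.41 to 3.86 against 2.25 is an illustration under assumed rates, not an estimate.

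Two stronger readings are tempting. One is that the window must dilute the effect. That follows if the effect builds gradually: a linear rise to 20 points, with stop days uniform over Days 28-97, gives 18.2, 16.3 and 14.5 points at 20%, 40% and 60% stopping. The documents give no time course, and early-stopper rates of 60% versus 20% push the odds ratio up. The other is that nearly all of an early stopper's final window is counted twice. Calendar overlap with Days 15-84 does average 91%, but the 12-day diary rule removes incomplete intervals and leaves 64% in the case worked above.

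Section 6 states that power is insufficient and efficacy is exploratory. The consequence is a primary estimate that cannot be read cleanly, not a confirmatory error. It is still worth correcting before unblinding, because it defines the primary outcome and the change is small.

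**What to change.** Before unblinding:

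- In Table 3 and 4.1.13, start the panic-free Week 11-12 interval for the repeated-measures odds ratio at Day 85 (Days 85-98, or to the last treatment day if later). Leave the outcome missing for participants who stopped earlier. This matches 5.11.1 and 5.13.
- State how stops on Days 85-95 are handled. Fewer than 12 on-treatment days then fall in the interval, so under the diary rule an attack is scored as failure while no attack becomes missing.
- Report the last-14-days-on-treatment outcome as a separately labelled while-on-treatment analysis with one record per participant. Include the 5.11.3 Fisher analysis there if it keeps its window. State in 5.11.2 that conclusions resting on the Fisher fallback answer that different question.
- Name the hypothetical strategy in Section 6.

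The cost is SAP wording and one derivation. There will be fewer observed Week 11-12 outcomes and a wider interval. The SAP should also say that an unweighted GENMOD (GEE) fit needs a stronger missing-data assumption than a likelihood-based model: broadly, that missingness does not depend on the participant's earlier outcomes. That is easier to defend for stops caused by the sponsor's closure than for stops due to adverse events or lack of efficacy.

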4.1.14. Diary Days

Diary days are defined as days with completed eDiary assessments, i.e. panic attack diary fields were recorded on that date.

4.1.15. Panic Attack Occurrence

Panic attack occurrence is defined as a panic attack eDiary entry associated with at least 4 panic attack symptoms. Associated field (CE.CEOCCUR) for event occurrence is recorded as either “Y” or missing.

4.1.16. eDiary Compliance

eDiary compliance will be calculated as 100 times the number of diary days (i.e., days with completed diary assessments) during a period divided by the expected number of completed diary days in that same period.

4.1.17. Compliance with Study Drug

Dosing compliance based on daily dose of IMP as recorded in the OVERALL DOSING - BLINDED CRF will be defined by the dosing compliance ratio: the number of doses actually taken by the participant divided by the number of doses that were expected to be taken during the same period multiplied by 100. Subjects were to have taken 4 tablets/day during the titration period and 2 tablets/day during the Maintenance Treatment Period.

4.1.18. Definition of Completed Participant

A participant is considered to be a treatment completer if he/she has completed the Treatment Period of the trial including the last visit in the Maintenance Treatment Period (Visit 6, Day 98) as captured in the eCRF.

A participant is considered to have completed the study if he/she has completed all periods of the trial including the last scheduled procedure in the Safety Follow-up (Visit 9, Day 131) as shown in the Schedule of Assessments in [Section 9.1](#) and as captured in the eCRF.

Table 3: Two-Week Intervals

Two-Week Interval	Study Days in Interval
Maintenance Week 1-2	Days 15-28
Maintenance Week 3-4	Days 29-42
Maintenance Week 5-6	Days 43-56
Maintenance Week 7-8	Days 57-70
Maintenance Week 9-10	Days 71-84
Maintenance Week 11-12 (no-panic attack endpoint)	Two weeks prior to end of treatment
Maintenance Week 11-12 (panic attack frequency endpoint)	Days 85-last day in treatment period

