### **9.3.3.2. Change From Baseline in Panic Attack Frequency During the Last 2 Weeks of the Maintenance Treatment Period**

The second key secondary estimand has the following attributes:

1. Treatments as randomized

2. The population defined by the inclusion/exclusion criteria of the trial as the primary population of interest
3. The change from baseline in panic attack frequency during the last 2 weeks of the Maintenance Treatment Period as the endpoint of interest
4. The population level summary of interest is the estimated treatment differences in median and the 95% Hodges-Lehmann CI
5. A composite strategy will be used to handle missing values due to ICEs. The cases of potential treatment-related ICEs described in [Section 9.3.3.1](#) will be assigned the worst rank and other cases of missing outcomes from ICEs will be assigned the second worst rank. The individual cases of treatment-related ICEs will be pre-identified prior to database lock.

The change from Baseline to each trial visit in frequency of panic attacks will be summarized by visit and treatment group. A non-parametric analysis using Mann-Whitney test performed on the change from Baseline during the last 2 weeks of the Maintenance Treatment Period will be the basis for comparison between the 2 treatment groups. A supportive analysis of frequency of panic attacks recorded at each visit will be performed using a Poisson or negative binomial regression with fixed effect of treatment group, visits, evidence-based psychotherapy use, and interaction between treatment group and visit. The Baseline panic attack frequency will be included as a covariate. Subject will be included as a random effect.

Sensitivity analysis will include all participants regardless of panic attack eDiary version used.

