3.1.1.1. Derivation of Panic Attack Frequency

For an event to meet the definition of a panic attack, the participant must report experiencing four or more of the symptoms described in the DSM-5-TR. Panic attack frequency is defined as the total number of panic attacks over each two-week interval divided by the total number of days the eDiary was completed in the same analysis period multiplied by 14. Participants with a minimum of 7 completed diary days in a two-week interval will be considered for panic attack frequency, otherwise will be considered missing.

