5.12.2. Second Key Secondary Efficacy Analysis

5.12.2.1. Estimand

The second key secondary estimand has the following attributes:

1. Treatments as randomized
2. Full analysis set as the primary population of interest
3. The change from baseline in panic attack frequency during the last two weeks of the Maintenance Treatment as the endpoint of interest
4. The population level summary of interest is the estimated treatment differences in median and the 95% confidence interval using Hodges-Lehmann estimation
5. While-on-treatment strategy with data prior to treatment discontinuation used in the analysis

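### SAP Table 3 starts the panic attack frequency window at Day 85, which conflicts with the stated while-on-treatment strategy and with one of the two definitions in SAP 4.1.13, and so leaves open who is analysed

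*SAP*

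**What the plan says.** SAP 5.12.2.1 gives the intercurrent-event strategy for this endpoint as "While-on-treatment strategy with data prior to treatment discontinuation used in the analysis", and the summary table in SAP 5.13 repeats it. The main test (SAP 5.12.2.2) is a Mann-Whitney comparison of change from baseline in the last two weeks of maintenance, with a Hodges-Lehmann interval.

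Three places determine who has a value:

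- **SAP Table 3** (printed under 4.1.18) has two rows for the final interval. For the panic-free endpoint the window is "Two weeks prior to end of treatment". For the frequency endpoint, in the row that begins "Maintenance Week 11-12 (panic attack frequency endpoint", it is "Days 85-last day in treatment period".
- **SAP 4.1.13** defines the last two weeks of maintenance twice. For an individual it is the 14 days ending with the last dose. For aggregate analysis it is the two weeks before Visit 6. It also requires at least 14 days of maintenance treatment.
- **SAP 3.1.1.1** sets the diary rule: "Participants with a minimum of 7 completed diary days in a two-week interval will be considered for panic attack frequency, otherwise will be considered missing". SAP 6 repeats the rule.

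Protocol 9.3.3.2 kept early stoppers in the test. Potential treatment-related cases were to be "assigned the worst rank and other cases of missing outcomes from ICEs will be assigned the second worst rank". SAP 6 discloses that this composite strategy was replaced, and it expects that, after the early closure, the "proportion of participants with treatment discontinuation will be increased".

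**The concern.** A while-on-treatment strategy uses what was observed up to the point of stopping. A window that opens on Day 85 has nothing to use from someone who stopped on Day 60, although that person kept a daily diary through several weeks of maintenance treatment. With the protocol's rank assignment gone, no imputation stated, and the only sensitivity analysis (SAP 5.12.2.3) concerned with eDiary version, nothing brings that person back into the main comparison.

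Two things are at stake. First, the same SAP supports two different analysis datasets, depending on whether the programmer follows Table 3 or the individual definition in 4.1.13. Second, if Table 3 is followed, the comparison is conditional on staying on treatment to about Day 91. That costs numbers in any case. It also introduces selection where stopping is related to outcome, for example stopping for adverse events or lack of efficacy, both of which Protocol 9.3.3.1 lists as potentially treatment-related.

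**Working it through.** **The plan's own figure.** The documents give no power or sample size for this endpoint. The only power statement (SAP 1.2) is for the primary: 114 per group, 60% versus 40%, at least 80%. It reproduces, at 86% by the normal approximation and 84% for Fisher's exact test. It is not in dispute and does not bear on this point.

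**Step 1: earliest evaluable last treatment day.**

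- Table 3: days in window = last treatment day − 85 + 1. At least 7 are needed, so last treatment day ≥ 85 + 7 − 1 = Day 91.
- SAP 4.1.13, individual definition: maintenance starts on Day 15 and 14 days are needed, so last dose ≥ 15 + 14 − 1 = Day 28.

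| Last treatment day | Days in Table 3 window | Value under Table 3? | Value under 4.1.13 individual definition? |
|---|---|---|---|
| 27 | 0 | no | no |
| 28 | 0 | no | yes |
| 60 | 0 | no | yes |
| 84 | 0 | no | yes |
| 90 | 6 | no | yes |
| 91 | 7 | only if all 7 are completed | yes |
| 98 | 14 | yes | yes |

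Each yes assumes at least 7 completed diary days. The two readings differ for stops on Days 28 to 90, which is 90 − 28 + 1 = 63 possible stop days.

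**Step 2: precision.** No stopping rate is given. Let f be the share stopping before Day 91, and assume that stop days are uniform over Days 1 to 90. The recoverable share of stoppers is then 63/90 = 0.70. The evaluable fraction is 1 − f under Table 3 and 1 − 0.3f under the individual definition. With interval width proportional to 1/√n, the current width relative to the width after the fix is √[(1 − 0.3f)/(1 − f)]. If every early stopper could be recovered, the ratio would be 1/√(1 − f), which is an upper bound.

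| f (assumed) | Evaluable now | Evaluable after fix | Width ratio | Upper bound |
|---|---|---|---|---|
| 0.20 | 0.80 | 0.94 | 1.08 | 1.12 |
| 0.40 | 0.60 | 0.88 | 1.21 | 1.29 |
| 0.60 | 0.40 | 0.82 | 1.43 | 1.58 |

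**Step 3: selection.** As an illustration only, take no true effect, 114 per arm, change distributed as normal with mean −4 and SD 5 in both arms, and stoppers chosen by poor outcome plus noise of SD 5. Over 2,000 simulated trials, dropping the stoppers gave rejection rates of 7%, 15% and 32% for stopping of 20% versus 20%, 30% versus 20% and 40% versus 20%, against a nominal 5%. Every one of those inputs is assumed. The result shows that unequal, outcome-related stopping can mislead this test, not that it does so in this trial.

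**The case against.** The strongest reply is that the SAP already contains the right window. The endpoint is worded as the last two weeks of maintenance treatment, and 4.1.13 defines that for an individual as the 14 days through last dose. On that reading early stoppers are in, and Table 3 is a slip. This has force: it shows that the SAP is inconsistent rather than uniformly based on Day 85. It does not settle the matter, because Table 3 names the frequency endpoint explicitly and the aggregate sentence of 4.1.13 agrees with it.

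Several stronger readings are tempting and go beyond the documents:

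- *The test is completers-only.* Not quite. Under Table 3, people stopping on Days 91 to 97 with 7 completed days stay in, and completers with fewer than 7 drop out.
- *Early stoppers' diaries are discarded.* They are lost only from the final-interval comparison. Table 3 has five earlier two-week intervals, SAP 5.12.2.2 summarises change by period, and SAP 5.15 applies the same methods at all time points.
- *The two Table 3 rows were swapped.* The contrast is odd, since the primary has the end-of-treatment window while its strategy for discontinuation is hypothetical. But nothing in the documents states that intent.
- *Dropping the protocol's worst ranks is itself an error.* SAP 6 discloses the change, and SAP 1 says that the SAP supersedes the protocol.
- *Everyone with any post-baseline diary should contribute.* That would override the 14-day maintenance minimum in 4.1.13 and admit people who stopped during titration to a maintenance endpoint.

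It is also fair that efficacy is now exploratory, that no multiplicity control remains (SAP 5.4), and that the closure was not associated with safety concerns (SAP 1). Stopping caused by the closure may be largely unrelated to outcome, and in that case it mainly costs precision.

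**Conclusion.** The point stands as an internal inconsistency that changes who is analysed. If Table 3 is followed, no one whose last treatment day is before Day 91 has a value in the main comparison. What is reported as while-on-treatment is then in effect an analysis of completers and near-completers. If the individual definition in 4.1.13 is followed, stops on Days 28 to 90 are kept.

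The precision cost is about 8%, 21% or 43% in interval width at 20%, 40% or 60% stopping before Day 91. It rests on assumed rates, assumed uniform stop days, and adequate diaries among those recovered. The figures of 12%, 29% and 58% are ceilings that a reader might take as the expected cost; the 14-day maintenance minimum keeps the real cost below them. Bias arises only to the extent that stopping is related to outcome, and the documents do not allow its size or sign to be stated. For one exploratory endpoint this should be corrected, but it does not undermine the plan as a whole.

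**What to change.** Before unblinding, reconcile SAP Table 3, 4.1.13 and 5.12.2.1:

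1. In Table 3 and in the aggregate sentence of 4.1.13, define the frequency window as each participant's last 14 days on treatment through last dose. Keep the 14-day maintenance minimum and the minimum of 7 completed diary days, and scale to 14 days as SAP 3.1.1.1 already does.
2. Keep Days 85 onward as a sensitivity analysis, described as completers and near-completers.
3. Report the number evaluable per arm under each window.

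If the sponsor prefers Day 85 for the main analysis, the estimand should be relabelled and an analysis that retains early stoppers added, such as the protocol's rank-based one.

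The cost is one table row, one sentence of 4.1.13 and the matching derivation, with no new data. The downsides are that time on treatment at assessment will vary between participants, which the while-on-treatment label already implies, and that those stopping before Day 28 remain excluded. If unblinding has already happened, SAP 6 provides for recording the change as a deviation in the clinical study report.
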